## Table 2General Definitions

Omadacycline (PTK 0796)

PTK0796-AP-17202 Statistical Analysis Plan

# 5.3 Missing Data and Data Imputation Methods

Missing data will be handled as outlined below

- 1. Adverse Events and Safety Data:
- All missing and partial dates for AEs will be queried for a value. If no value can be obtained, substitutions will be made as detailed in Section 8.4. These substitutions will be used in calculations; however, the actual value recorded on the eCRF will be used in all listings.
- If the time of the first dose of test article is missing, it will be imputed with time of randomization + 1 minute. If time is missing for other doses it will be imputed with time of previous dose + 12 h.
- An AE is considered treatment emergent if the AE start date and time is on or after the start date and time of the first dose of test article.
- If time of the AE is missing and it occurred on the same date as the first dose of test article, the AE will be defined as treatment emergent. If the start date of the AE is partial or missing and it cannot be determined if the AE occurred prior to or after the first dose of test article, the AE should be defined as treatment emergent. Appendix 4 Adverse Event Start/Stop Date Imputation provides imputation for partial or missing date information. For AE listings, all dates and times will be displayed as reported on the Case Report Forms.
- If no value can be obtained for all other times for events and assessments occurring after randomization, the time will not be imputed but will remain missing.
- The severity and causality assessment for AEs cannot be missing. Missing data will be queried for a value. The highest severity and most related causality should be used if query is missing. If query will return missing, then the highest severity and most related causality will be used for the purpose of summaries.
- If the reported value of a clinical laboratory parameter cannot be used in a statistical summary table (e.g., a character string is reported for a parameter of the numerical type), a coded value must be appropriately determined and used in the statistical analyses. A value that is in the lower limit of the normal range will be calculated as 99.99% of the value if it is reported as "<" (e.g. <5 will be converted to 5\*0.99=4.9995). A value that is in the upper limit of the normal range will be converted to 100.01% if it is reported as ">" (e.g.>7 will be converted to 7\*1.001=7.007). However, the actual values as reported in the database will be presented in data listings.
- Prior and Concomitant Medication start date imputation will be imputed according to table in Appendix 4 Concomitant Medication Start Date Imputation.
- 2. Efficacy Data
- Analysis of efficacy data will be based on the available data, unless otherwise stated.
- Missing data for clinical and microbiological outcomes is denoted "indeterminate", unless any of the below rules apply.
- Missing microbiological outcomes at EOT will be imputed by last day of test article intake.
- The Overall Clinical Response at PTE and FFU visits are derived based on the "worst case scenario" to accommodate for missing visit assessments and intercurrent events (eg rescue

93 Version: 1.0 Status: Approved Approved Date: PTK0796-AP-17202 Statistical Analysis Plan

Omadacycline (PTK 0796)

Paratek Pharma, LLC

PTK0796-AP-17202 Statistical Analysis Plan

medication at EOT visit). Similar imputations were applied to microbiological response endpoints. Details are described in Section 7.

• mPSAQ data for bothersome score will be imputed with score of 0 for each question for which severity is answered "Did not have".

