## 7.6 Test Article Administration

### 7.6.1 Intravenous Treatment Phase

The iv treatment phase (minimum 1 day, 1 dose) will follow a double-blind design for omadacycline and levofloxacin. Infusions of both test articles will be administered continuously over approximately 90 minutes. All infusion start and stop times are to be recorded in the source documents and on the eCRF. Because the color of the test article and placebo infusions are different, all infusion bags and iv tubing will be covered with materials provided by the sponsor (as described in the Pharmacy Manual) so that subjects and blinded study personnel will not know the identity of the test article being administered. Subjects in each study arm will receive the same infusion volumes with the same blinded administration instructions. All iv infusions will be administered by qualified blinded personnel. However, unblinded personnel may administer the iv infusions provided they will not be performing

any efficacy assessments. If gravity administration is not the standard of care then an infusion pump may be used. If an infusion pump is used then an unblinded administrator will be required.

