### 7.6.2 Selection and Timing of iv Dose for Each Subject

To facilitate study enrollment at all times of the day and permit subjects to be “shifted” to a more practical dosing schedule consistent with hospital schedules, provision is made for limited adjustment of the dosing interval. Specifically, infusion times may be adjusted up to  $\pm 2$  hours per infusion interval until the desired administration schedule is achieved.

Once the desired start of infusion time is determined, subsequent infusions should be “anchored” to that time. That is, thereafter, the start of infusion should be within  $\pm 1$  hour of the specified target infusion time.

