### 7.6.3 Management While on iv Test Article

While the subject is receiving iv therapy, the investigator will assess the subject daily and choose one of the following outcomes based on the overall clinical response of the subject:

- Continue iv test article
- Assess for po test article using the protocol defined criteria (after a minimum of 1 days [1 doses] of iv therapy), see [Section 7.6.5](#). Note, the first po dose should be administered in the morning, 12 to 24 hours after the last dose of iv test article.
- Discontinue test article – this decision will prompt the EOT evaluation (even if the subject does not complete the minimum of 7 days of dosing)

Subjects who meet the criteria and are switched to po test article administration will continue to receive iv infusions throughout their treatment phase in order to maintain the blind. Subjects randomized to an IV only treatment group will continue to receive active IV treatment and placebo po treatment. Subjects randomized to an IV/PO treatment group will receive placebo IV and active po treatment. At all times during the study the decision to continue iv, switch to po, or discontinue test article is made based on the clinical judgment of the investigator. Each daily decision is to be recorded on source documents and the information transferred to eCRFs by blinded study site personnel.

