#### 7.6.5 Investigator's Decision to Switch from iv to po Treatment

Initially, all randomized subjects will receive at least 1 day of iv antibacterial therapy. Beginning on the day 2 visit, the subject may be eligible to switch from iv to po therapy.

Switch from active iv to active po study drug therapy is optional, and will occur based on treatment group assigned. Upon decision to switch, subjects randomized to iv only groups will begin to receive placebo po in addition to their active iv test article. Those in an iv/po group will begin to receive active po test article and placebo iv infusions. The decision should be made by the investigator based on evaluation of the criteria below. Criteria will be confirmed and documented in source documents:

- Afebrile for  $\geq 24$  hours (highest daily oral, tympanic, rectal, or core temperature  $< 37.8^{\circ}\text{C}$  [ $100.0^{\circ}\text{F}$ ]) without the use of anti-pyretics,
- Improvement or resolution of the signs and symptoms of the index AP,
- Ability to tolerate and ingest oral therapy (eg, no nausea, vomiting), and
- For subjects with baseline bacteremia, follow-up blood cultures must be negative.

Subjects who are switched to po test article administration will continue to receive iv infusions in order to maintain the blind. Switch to po will not be permitted until after the subject has completed at least the first day of iv treatment (after 1 dose). The date and time the investigator confirmed the criteria for the subject's eligibility for po treatment were met and made the decision to switch to po treatment will be recorded on source documents and the information transferred to eCRFs by study site personnel.

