#### 7.6.6 Oral Treatment Phase

When switching from iv to po test article the recommended interval between doses will be maintained. The first po dose, for both omadacycline and levofloxacin treatment arms, should be given in the morning 12 to 24 hours after the last dose of iv test article.

The po treatment phase will employ a double-blind, double-dummy design using omadacycline placebo comparator tablets of matching size and shape to active omadacycline tablets and matching over-encapsulated placebo and active levofloxacin tablets.

To maintain investigator and subject blinding, subjects in both arms will receive both tablets and over-encapsulated tablets during each dose. Subjects in groups 1 and 2 will receive placebo omadacycline tablets and placebo over encapsulated levofloxacin tablets. Subjects in groups 3, 4 and 5 will also continue to receive iv placebo infusions to maintain the blind.

The po treatment will be administered by study staff during visit assessments.

All doses of oral test article should be taken with water.

All oral doses should be taken in a fasted state. Fasting is defined as no food, antacids or multivitamins containing multivalent cations (eg, aluminum, magnesium, calcium, bismuth, iron, or zinc) or drink except water for at least 6 hours before dosing. After dosing, no food is permitted for 2 hours as well as no dairy products, antacids or multivitamins containing multivalent cations (eg, aluminum, magnesium, calcium, bismuth, iron, or zinc) for 4 hours.

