### Table 1Description of Treatment groups

iv = intravenous, po = per oral;

Note: dosing in all treatment groups is once-per-day:aThe total duration of treatment for subjects is 7-10 days, up to 14 days of treatment for subjects with bacteremia.

All eligible subjects will be randomized via an Interactive Response System (IxRS) that assigns them to the treatment arm. The site delegate will contact the IxRS after confirming that the subject fulfills all the inclusion criteria and has none of the exclusion criteria. The IxRS will assign a test article to the subject based on a computer-generated randomization schedule. The randomization will be a blocked randomization sequence as defined in the IxRS specifications.

It is possible that not all treatment arms will be enrolling subjects at the same time. Arms may be dropped based on DMC recommendations. There will always be at least one omadacycline arm and the levofloxacin arm open.

Subjects randomized into the study will be assigned the treatment corresponding to the next available number from the computer-generated randomization schedule. The subject is considered randomized when the IxRS provides the test article assignment, regardless of whether the subject actually receives any medication. As this is an adaptive design trial, any updates to the randomization schedule based on DMC recommendation and will be incorporated into the IxRS system.

The investigator and sponsor will be blinded to treatment arm assignments. The iv and po phases of the study will be double-blind.

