## PTK0796-AP-17202 Statistical Analysis Plan

During the po phase, a double-blind, double-dummy design will be used to ensure the blind is maintained. Subjects on the omadacycline arms may receive active omadacycline tablets and over-encapsulated levofloxacin placebo tablets. Subjects on the levofloxacin arm will receive omadacycline placebo tablets and over-encapsulated active levofloxacin tablets. Infusions will be administered concomitantly along with the po treatment to maintain the overall study blind.

Data that could potentially lead to unblinding will not be accessible to anyone other than the following site personnel:

- unblinded study pharmacist or designee
- unblinded study monitor
- unblinded administrator(s)

Unblinding is only to occur in the case of subject emergencies and at the conclusion of the study.

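### SAP 5.3 imputes missing later dose times at 12 h although every arm is dosed once daily; secondarily, the prior-antibiotic item in SAP 4.4 has an ambiguous criterion number

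*SAP*

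**What the plan says.** **Dose times.** SAP 5.3 has two rules. A missing time for the first dose becomes the time of randomization plus one minute. For every later dose, "If time is missing for other doses it will be imputed with time of previous dose + 12 h". The trigger is a missing time. The SAP does not say whether a recorded dosing date is kept.

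**Schedule.** The note to SAP Table 1 states that "dosing in all treatment groups is once-per-day", and protocol Table 1 agrees. For infusions, protocol 7.6.2 says that "provision is made for limited adjustment of the dosing interval": up to 2 h either way per interval until the wanted schedule is reached, then within 1 h of the target. At the change of route, protocol 7.6.3 says "the first po dose should be administered in the morning, 12 to 24 hours after the last dose of iv test article", and 7.6.6 gives the same window for both drugs. After the change, SAP 3.3 says: "Infusions will be administered concomitantly along with the po treatment to maintain the overall study blind".

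**What is recorded.** Protocol 7.6.1: "All infusion start and stop times are to be recorded in the source documents and on the eCRF". Protocol 7.6.5 says that the date and time the investigator confirmed eligibility and "made the decision to switch to po treatment will be recorded on source documents and the information transferred to eCRFs by study site personnel".

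**Clinically evaluable (CE) population.** SAP 4.4 requires subjects to satisfy every listed criterion. Item 3a, on prior antibiotic therapy, reproduces protocol exclusion 2. Its closing sentence then removes from CE the subjects who meet exclusion 5, which in protocol 6.3 is symptoms lasting more than 7 days. The only other list of exclusions in SAP 4.4 covers numbers 6 to 15.

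**The concern.** A 12-hour step is the interval of a twice-daily regimen, and no arm here has one. SAP section 1 lets the SAP prevail over the protocol, so a programmer would have to code the 12 h as written, and SAP section 9 does not list it as a deliberate change.

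Three planned outputs can take in a later dose time:

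- SAP 5.4: when several on-treatment measurements fall on one day, the one nearest the start of dosing is used.
- SAP 8.2: time to oral switch, counted in 24-hour periods.
- SAP 8.4: adverse events starting on iv treatment against those starting after the switch, for the arms that can switch (Groups 3, 4 and 5, so 3 of 5). Nausea and vomiting, which the protocol synopsis names as adverse events of interest, fall within this table.

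The second and third depend on a definition that SAP 8.2 and 8.4 omit: whether the switch is the time of the first tablet or the time of the decision recorded under protocol 7.6.5.

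For SAP 4.4, what is at stake is CE membership, and with it the microbiologically evaluable (ME) population, for enrolled subjects who violated exclusion 2 or 5.

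**Working it through.** **1. The stated interval.** Once daily gives 24 h / 1 dose = 24 h. The SAP's 12 h is not reproduced; it would need 24 / 2.

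**2. Against the permitted intervals, taking the imputed date and time as they fall.**

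| Step | Permitted or nominal gap | Imputed gap | Shortfall |
|---|---|---|---|
| iv to iv | 24 − 2 = 22 h to 24 + 2 = 26 h | 12 h | 10 to 14 h |
| tablet to tablet | 24 h nominal | 12 h | 12 h |
| last iv to first tablet | 12 to 24 h | 12 h | 0 to 12 h |

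Once infusions are anchored, two successive starts, each within 1 h of target, again give 24 − 1 − 1 = 22 h to 24 + 1 + 1 = 26 h. The rule falls inside the permitted range only in the last row, at its lower end. If k consecutive times are missing, the shortfall is 12k h: 12, 24, 36 h for k = 1, 2, 3.

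**3. If the recorded date is kept.** Previous dose 08:00 on Day 2, Day 3 time missing:

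- date and time as they fall: 20:00 on Day 2, which contradicts the Day 3 record;
- date kept: 20:00 on Day 3, a 36 h gap, 12 h late against 08:00.

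With a previous dose at 14:00, both readings give 02:00 on Day 3, 12 h early. With the date kept, the direction therefore depends on whether the previous dose was before noon.

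**4. Which dose is the previous one.** After the switch, infusion and tablets are given together. If a tablet's previous dose is taken to be that day's infusion, the rule places the tablet 12 h after an infusion that it accompanied.

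**5. Effect on the switch outputs, assuming that the switch is the first tablet.** Infusions at 08:00 on Days 1 and 2; first tablet at 08:00 on Day 3, time missing.

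- True time to switch: 48 / 24 = 2.0 periods.
- Date not kept: 36 / 24 = 1.5. Nausea at 06:00 on Day 3, before the tablet, is counted as oral-phase.
- Date kept: 60 / 24 = 2.5. Nausea at 10:00 on Day 3, after the tablet, is counted as iv-phase.

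If the switch is the decision time, neither output moves. The SAP 5.4 choice does not depend on this definition.

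**6. Outputs based on the first dose or on dates.** Treatment-emergent status uses the first dose, which has its own rule, so it does not change. Compliance divides doses received by doses expected between the first infusion date and the last dose date. It changes only if an imputed time may move that last date. As an illustration, 5 of 7 is 71.4% and 5 of 6 is 83.3%, on either side of the 80% required for CE.

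**7. With + 24 h.** For infusions the error is |22 − 24| = 2 h at one end and |26 − 24| = 2 h at the other, so 0 to 2 h.

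**8. SAP 4.4 item 3a.** Three readings are open:

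- A, only the closing sentence excludes: exclusion 5 out of CE, exclusion 2 in.
- B, exclusion 2 applies because it is listed, and 5 is added: both out.
- C, the 5 is a slip for 2: exclusion 2 out, exclusion 5 in.

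Exclusion 5 is not redundant. Inclusion 3 accepts worsening within 96 h (4 days), so symptoms of more than 7 days that recently worsened can still satisfy it.

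**The case against.** **The 12 h may be meant for the switch dose.** It lies in the protocol's window for the first tablet, and that is the dose on which the switch outputs depend. This stands for that dose only. SAP 5.3 applies to all later doses, and after an 08:00 infusion + 12 h gives 20:00, although the first tablet is to be given in the morning.

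**The rule will seldom be used.** Infusion times go on the eCRF, staff manage all dosing (protocol 7.15), and clock times of dosing are entered for the pharmacokinetic samples (8.11). The larger errors, between infusions or between tablets, reach no planned output except the SAP 5.4 choice, unless an imputed time may move the last dose date. SAP 8.2 also reports the day of switch separately. All of this stands, and it keeps the point small.

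**Item 3a may contain no error.** SAP 4.4 applies inclusion criteria 2 to 4 simply by restating them, and exclusion 2 can work the same way. Reading B is then coherent under a heading too narrow for its content. SAP 4.4 also leaves allocation details to the Pathogen and CE Review Plan, which was not available here. A reader might infer that pre-treated subjects are left in CE; the text does not show that. What remains is a cross-reference with more than one reading.

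**Conclusion.** The 12 h rule is wrong as written for every compliant iv-to-iv dose and, at the nominal interval, for every tablet-to-tablet dose. The size is 10 to 14 h between infusions and 12 h between tablets. For the first tablet it is 0 to 12 h, or up to 12 / 24 = 0.5 of a period in time to switch, when date and time are used as they fall. These figures assume dosing within the protocol's windows. The number of missing times is not given.

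Several stronger inferences are tempting, and the documents do not carry them:

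- That imputed doses are always early: with the recorded date kept they can be late.
- That everything depends on the definition of the switch: SAP 5.4 uses dose time regardless.
- That compliance is safe because it is counted by date: this holds only if an imputed time cannot move the last dose date.
- That efficacy is biased: membership of ITT and micro-ITT does not depend on either item, SAP 7.1 treats all efficacy endpoints as exploratory, and nothing indicates a direction.

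The point is a minor correction. Item 3a is secondary: passages to reconcile, with no omission shown. Both criteria bar entry, so only enrolled violators are affected, and their number is not given.

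**What to change.** **SAP 5.3.** Keep the recorded dosing date and impute only the clock time, as the previous dose of the same route + 24 h. For the first tablet, use the clock time of the same-day infusion if recorded, otherwise the clock time of the previous infusion. Say that both are approximations. The infusion is only given alongside the tablet. In the second case, a tablet taken the next day 12 to 24 h after the last infusion would be placed 24 − 24 = 0 to 24 − 12 = 12 h late. The recorded switch-decision date and time should not stand in for the tablet time, because the decision can fall on an earlier date than the dose.

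**SAP 8.2 and 8.4.** Add one sentence to each saying whether the switch is the first-tablet time or the decision time.

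**SAP 4.4 item 3a.** State whether exclusion 2, exclusion 5 or both remove a subject from CE. If 5 is intended, list it as its own criterion. Make this agree with the Pathogen and CE Review Plan before unblinding.

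**Cost.** A few sentences and the matching code. No new data are needed: infusion times and the switch decision are already collected.

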### 5.4 Visit Windows

Subjects will participate in the study for up to 30 days. Following Screening, eligible subjects will be randomly assigned to receive 7 to 10 days of iv/po treatment of either omadacycline or levofloxacin. Subjects with bacteremia confirmed from local blood culture drawn at screening can receive up to 14 days of treatment. Subjects will return to the site for an EOT visit on the day of or within 2 days following the last dose of test article. Subjects will return to the study site for a PTE on Day 21 ( $\pm$  2 days). A final follow-up assessment will be conducted Day 28 ( $\pm$  2 days) following the first dose of test article. A tabular summary of the visit schedule is displayed in Table 3.

Study Visit	Study Day	Notes
Baseline	Day -1 or Day 1	Except where indicated, last measurement prior to the first dose of test article. Screening assessments are to be taken within 24 hours prior to randomization if no test article is taken, the date and time of randomization is used in place of randomization date.
On Treatment (note: analysis visit will be each Study Day)	Day 1 to Day 7 Day 8 to Day 14 (latest on treatment Day)	As entered in the eCRF for these visits
EOT	Not later than Day 16	Within 2 days following the last dose of test article
PTE	Day 21	On Day 21 ( $\pm$ 2 days) after the subject's first day of test article
Final Follow-up (FU)	Day 28	On Day 28 ( $\pm$ 2 days) after the subject's first day of test article

#### Table 3Scheduled Study Visits

Study Day is calculated relative to the first dose of test article (Day 1); there is no Day 0 – the day prior to the first dose of test article is Day -1. If no test article is taken, study day is calculated relative to the date of randomization.

For efficacy outcomes, the data collected at the EOT, PTE and FFU visits, regardless of when these occur will be utilized in the analysis in the ITT and micro-ITT population. The CE and ME populations exclusions due to windowing are outlined in Sections 4.4 and 4.5.

For each safety outcome and UTISA data, analyses will utilize assessments occurring during the scheduled visit windows (provided in Table 3). Thus, if a subject has a visit outside the scheduled visit window, for example, a PTE Visit occurred 20 days after the subject's first investigational product dose, the assessment will not be summarized with the PTE Visit but will be considered an unscheduled assessment. If a subject does not have an assessment at a scheduled visit and an unscheduled assessment was taken within the window for the time point (for example, 21 days ( $\pm$  2 days) after the subject's first day of therapy for PTE), these assessments will be summarized in the by time point analyses. If more than one measurement is

93 Version: 1.0 Status: Approved Approved Date: PTK0796-AP-17202 Statistical Analysis Plan

Omadacycline (PTK 0796)

PTK0796-AP-17202 Statistical Analysis Plan

taken during the visit window, the value taken on the scheduled visit will be utilized or if no scheduled visit was done, the first (earliest) measurement in the visit window will be used. If more than one measurement is taken on the same day, the assessment closest to the start of the dose will be used for on treatment values and the last measurement on the day will be used for post-treatment values. For worst overall post-baseline analyses, all assessments including those obtained from unscheduled visits will be included.

